#### **4.2. Variable Definitions**

The following variables will only be calculated if not reported on the eCRF.

##### **4.2.1. Age**

Subject age will be calculated as the integer part of the number of years from date of birth to the date of signing the informed consent form, using the following formula:

$$\text{Age} = \text{integer part of } (\text{date of informed consent} - \text{date of birth} + 1) / 365.25$$

##### **4.2.2. Body Mass Index**

Body mass index (BMI) will be calculated as follows:

$$\text{BMI (kg/m}^2\text{)} = [\text{weight (kg)}] / [\text{height (m)}]^2$$

##### **4.2.3. Prior and Concomitant Medication**

Prior medication is defined as any nonstudy drug started before the first dose of study drug.

Concomitant medication is defined as any nonstudy medication that is started accordingly:

- Before the date of first administration of study drug and is ongoing throughout the study or ends on/after the date of first study drug administration.
- On/after the date of first administration of study drug and is ongoing or ends during the course of study drug administration.

A prior medication could also be classified as "both prior and concomitant medication" if the end date is on or after first dose of study drug. In the listing, it will be indicated whether a medication is prior-only, concomitant-only, or both prior and concomitant medication.

For the purposes of analysis, all medications will be considered concomitant medications unless the medications can unequivocally be defined as not concomitant.

## **5. STATISTICAL METHODOLOGY**

### **5.1. General Methodology**

Unless otherwise noted, SAS® software (SAS Institute Inc, Cary, NC; version 9.1 or later) will be used for the generation of all tables, graphs, and statistical analyses. Descriptive summaries for continuous variables will include, but not be limited to, the number of observations, mean, standard deviation, median, minimum, and maximum. Descriptive summaries for categorical variables will include the number and percentage of subjects in each category. [REDACTED]

### **5.2. Treatment Groups**

This is a randomized, double-blind, and parallel treatment group design. Subjects will be summarized by treatment groups. For subjects who crossed over to ruxolitinib from anagrelide, applicable efficacy and safety will be summarized separately.

### **5.3. Analysis Populations**

#### **5.3.1. Intent-to-Treat Population**

The intent-to-treat (ITT) population will include subjects randomized in the study. Treatment groups for this population will be defined according to the treatment assignment at the time of randomization.

The ITT population will be used for the summary of demographics, baseline characteristics, subject disposition, and analyses of all efficacy data.

#### **5.3.2. Per Protocol Population**

The per protocol (PP) population will include those ITT subjects who are considered to be sufficiently compliant with the Protocol.

The following procedures will be performed to identify those subjects who are to be excluded from the PP population before the database freeze:

- Clinical review of Protocol deviations/violations.
- Clinical review of concomitant medications as defined in Section 5.6 of the Protocol.
- Clinical review of the dose administration and drug accountability listing.

Subjects who do not meet the criteria for ET diagnosis or hydroxyurea resistance/intolerance (inclusion criteria 2 and 3; refer to Section 3 of the Protocol) and subjects who are < 80% compliant during the primary endpoint assessment period (Weeks 32-52) as determined by drug accountability assessment will be excluded from per protocol population.

The determination of subjects being considered for exclusion from the PP population by the clinical team will be prepared and signed before database freeze.

The PP population will be used in the supportive sensitivity analyses for efficacy endpoints.

### 5.3.3. Safety Population

The safety population includes all randomized subjects who received at least 1 dose of study drug. All safety analyses will be conducted using the safety population.

[REDACTED]

## 6. BASELINE, EXPOSURE, AND DISPOSITION VARIABLES AND ANALYSES

[Appendix F](#) provides a list of data displays.

### 6.1. Demographics and Baseline Characteristics, and Disease History

#### 6.1.1. Demographics

The following demographics will be summarized for the ITT population: age, sex, race, ethnicity, weight, height, and BMI.

#### 6.1.2. Baseline Characteristics

The following baseline disease characteristics will be summarized for the ITT population: baseline platelet counts, baseline WBC counts, baseline hematocrit, [REDACTED], JAK2V617F mutation status (positive vs negative), prior anagrelide use (yes vs no), MPL mutation status, CALR mutation status, triple-negative status, [REDACTED], and ECOG status ([Appendix B](#)).

#### 6.1.3. Disease History

Time since initial diagnosis, number of prior systemic therapies, prior thrombosis, and prior hemorrhage and cardiovascular (CV) risk factors including smoking, hypertension, hypercholesterolemia, and diabetes will be summarized for all the subjects in the ITT population.

Time since diagnosis will be calculated as follows:

$$\text{Time since diagnosis (years)} = (\text{date of randomization} - \text{date of diagnosis} + 1) / 365.25$$

#### **6.1.4. Prior Therapy**

Number of subjects who received prior systemic therapy for ET will be summarized for the ITT population. Drug name, start and stop dates, best response, and reason for discontinuation will be listed.

#### **6.1.5. Medical History**

For subjects in the ITT population, medical history will be summarized by system organ class and preferred term and will be listed.

### **6.2. Disposition of Subjects**

The number and percentage of subjects who were randomized, were treated, discontinued the randomized treatment before and after unblinding with a primary reason for discontinuation, crossed over to ruxolitinib from anagrelide, discontinued ruxolitinib after crossing over with a primary reason for discontinuation, and withdrew from the study before and after unblinding with a primary reason for withdrawal will be summarized for the ITT population.

### **6.3. Protocol Deviations**

Protocol deviations collected on eCRF will be presented in the subject data listings.

### **6.4. Exposure**

For subjects in the safety population, exposure to ruxolitinib/anagrelide will be summarized descriptively as the following:

- **Duration of treatment with ruxolitinib/anagrelide:**

Duration of treatment (weeks) = [date of last dose of ruxolitinib/anagrelide – date of first dose of ruxolitinib/anagrelide + 1]/7

- **Average daily dose of ruxolitinib/anagrelide:**

Average daily dose of ruxolitinib/anagrelide (mg/day) = total actual ruxolitinib/anagrelide dose taken (mg) / duration of treatment with ruxolitinib/anagrelide

- **Dose modifications:**

Number of subjects who had ruxolitinib/anagrelide dose reduction, escalation, and interruption will be summarized.

Exposure to ruxolitinib for subjects who crossed over to ruxolitinib from anagrelide will be summarized separately.

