## 4. INVESTIGATIONAL PLAN

### 4.1. Overall Study Design

[figure not shown]
This is a Phase 2, randomized, double-blind, double-dummy study in subjects with ET who are resistant to or intolerant of HU (according to modified ELN criteria) with a screening platelet count  $\geq 650 \times 10^9/L$  and WBC count  $\geq 11.0 \times 10^9/L$ . Subjects will be randomized in a 1:1 ratio, stratified by JAKV617 mutation status (positive vs negative), platelet count at screening ( $\geq 1000 \times 10^9/L$  or  $< 1000 \times 10^9/L$ ), and prior anagrelide use (yes vs no) to the following 2 treatment groups:

- Group A: ruxolitinib at a dose of 10 mg BID orally and anagrelide-placebo.
- Group B: anagrelide at a dose of 1 mg BID orally and ruxolitinib-placebo.

The study will enroll approximately 120 subjects. Due to block randomization and stratification, the 2 treatment groups may not each contain exactly the targeted number of subjects (n = 60).

Subjects will receive blinded study treatment for 52 weeks. Options for the open-label treatment phase are detailed in Section 4.1.1. All subjects will be followed for safety (eg, reporting of AEs and SAEs) 30 to 37 days after the last dose of blinded study treatment or open-label study treatment. The overall study design is shown in Figure 1.

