### 5.4.1. Dose Increases for Inadequate Efficacy

Dose increases will be permitted for inadequate efficacy. Dose increases for subjects meeting prespecified criteria for inadequate efficacy will be permitted after 2 weeks of therapy, and dose decreases for safety are allowed at any time. Doses of both study drugs will be titrated simultaneously using different dose levels as shown in [Table 2](#). Anagrelide or anagrelide placebo and ruxolitinib or ruxolitinib placebo increases are permitted per investigator discretion and taking into account the manufacturer's instructions, labeling, and subject's medical condition.

Each dose escalation must be at least 1 week apart, and subjects must meet all of the following criteria:

1. Platelet count  $\geq 150 \times 10^9/L$
2. Hemoglobin  $\geq 9$  g/dL.
3. ANC  $\geq 1500 \times 10^9/L$ .
4. One or more of the following:
  - a. Platelet count  $> 600 \times 10^9/L$ .
  - b. WBC count  $> 10 \times 10^9/L$ .
  - c. Minimal improvement, no change, or worsening of vasomotor symptoms including headache, lightheadedness, syncope, atypical chest pain, acral paresthesia, livedo reticularis, erythromelalgia, and transient visual disturbances (eg, amaurosis fugax, scintillating scotomata, ophthalmic migraine).

Additionally, it is recommended that safety hematology be performed within 14 days of a dose increase to confirm that a safe dose has not been exceeded. Doses may be increased by 5 mg BID for ruxolitinib or ruxolitinib-placebo. These are per investigator discretion and taking into account the manufacturer's instructions, labeling, and subject's medical condition. The dose of ruxolitinib or ruxolitinib-placebo will never exceed 25 mg BID.

Doses of anagrelide or anagrelide placebo may not be increased by more than 0.5 mg/day per week from the previous dose or to a dose that was not previously tolerated by the subject. The dose of anagrelide or anagrelide placebo should not exceed 2.5 mg BID (and 2.5 mg in a single dose). The maximum dose of anagrelide is 2.5 mg BID (5 mg total per day), which corresponds to a high maintenance dose used in practice.

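### SAP 6.4 divides total dose by a duration in weeks and labels the result mg/day, so average daily dose as written comes out seven times too high

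*SAP*

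**What the plan says.** SAP Section 6.4 lists three descriptive exposure summaries for the safety population: duration of treatment, average daily dose and dose modifications.

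- The duration formula begins "Duration of treatment (weeks) = [date of last dose of ruxolitinib/anagrelide" and, after the minus sign, ends "date of first dose of ruxolitinib/anagrelide + 1]/7". The unit is therefore weeks.
- The next bullet reads "Average daily dose of ruxolitinib/anagrelide (mg/day) = total actual ruxolitinib/anagrelide dose taken (mg) / duration of treatment with ruxolitinib/anagrelide". Its denominator repeats, word for word, the heading of the weeks formula, and its result is labelled mg/day.

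The SAP text defines no duration of treatment in days, and the average-dose formula contains no factor of 7. Section 6.4 also asks for a separate summary of ruxolitinib exposure in subjects who cross over. In the list of planned tables, Table 3.1.1 (study drug exposure and compliance, randomized phase) is marked for in-text use, and Table 3.1.2 covers exposure in the all-ruxolitinib phase.

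**The concern.** The two formulas do not fit together dimensionally: total mg over weeks gives mg per week, and the SAP calls it mg per day.

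Both drugs are titrated in this trial. Protocol Table 2 runs from 5 to 50 mg/day for ruxolitinib and from 0.5 to 5 mg/day for anagrelide. Of the three summaries in Section 6.4, average daily dose is the only one that says how much drug subjects took. A sevenfold error there would misstate exposure in both arms, and at most dose levels it would make subjects appear to have been dosed above the protocol maximum.

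**Working it through.** The plan states no average dose to reproduce, so the check is of units, followed by worked examples set against the protocol's own daily doses.

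**Inputs**

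- Duration and average-dose formulas: SAP 6.4.
- Blinded treatment length: "Subjects will receive blinded study treatment for 52 weeks" (Protocol 4.1). 52 × 7 = 364 days.
- Starting doses (Protocol 4.1): "ruxolitinib at a dose of 10 mg BID orally and anagrelide-placebo", which is 20 mg/day, and "anagrelide at a dose of 1 mg BID orally and ruxolitinib-placebo", which is 2 mg/day.
- Maximum doses (Protocol 5.4.1): "The dose of ruxolitinib or ruxolitinib-placebo will never exceed 25 mg BID", which is 50 mg/day; for anagrelide 2.5 mg BID, which is 5 mg/day.
- Lowest dose level (Protocol Table 2, DL -3): ruxolitinib 5 mg/day, anagrelide 0.5 mg/day.

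**Algebra**

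Let T be the total mg taken and D = last dose date − first dose date + 1, in days.

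- Duration as defined: W = D/7 weeks.
- Average dose as written: T/W = 7T/D.
- Average dose in mg/day: T/D.
- Ratio: (7T/D)/(T/D) = 7, whatever the dose, duration or arm.

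**Examples, constant dose for 364 days (52 weeks)**

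| Drug and level | Total mg | As written (total/52) | Per day (total/364) |
|---|---|---|---|
| Ruxolitinib, start | 20 × 364 = 7280 | 140 | 20 |
| Ruxolitinib, maximum | 50 × 364 = 18200 | 350 | 50 |
| Ruxolitinib, lowest | 5 × 364 = 1820 | 35 | 5 |
| Anagrelide, start | 2 × 364 = 728 | 14 | 2 |
| Anagrelide, maximum | 5 × 364 = 1820 | 35 | 5 |
| Anagrelide, lowest | 0.5 × 364 = 182 | 3.5 | 0.5 |

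The last column matches the total daily doses in Protocol Table 2; the third does not. Early stopping does not change the ratio. At ruxolitinib 20 mg/day for 100 days, 2000/(100/7) = 140, against 2000/100 = 20.

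**Would the wrong value look wrong?** An as-written value stays within the protocol maximum only if the true average is at most 50/7 = 7.1 mg/day for ruxolitinib or 5/7 = 0.71 mg/day for anagrelide. Among the Table 2 levels only the lowest qualifies. The next one up (10 and 1 mg/day) gives 70 and 7, both above the maximum.

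**The case against.** The strongest reply is that days were plainly meant. The quantity is called a daily dose and labelled mg/day, the weeks unit is attached only to the displayed duration formula, and the denominator carries no unit of its own. A programmer would probably read it as days. If not, 140 mg/day against a maximum of 50 should be caught at table review. Nothing inferential depends on the result either. Compliance in SAP 6.5 is mg over mg, so the 80% compliance rule for the per protocol population does not rely on this formula, and average dose enters no efficacy test or adverse event summary. Because the factor is constant, comparisons within one drug are preserved.

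Most of this stands as a limit on impact. The documents contain no results and no exposure code, so the error is what follows from literal programming; it is not a reported misstatement. The reply does not remove the defect. The denominator names the quantity just defined in weeks, and no other duration of treatment is available. A programmer who silently corrects it produces output that no longer follows the SAP, and an independent programmer working from the text would get a different number. Detection by eye is likely but not assured, since subjects held near the lowest dose level would show values inside the permitted range.

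**Conclusion.** The point holds. As written, SAP 6.4 yields mg per week under a mg/day label, exactly 7 times the average daily dose, for every subject in both arms: 140 instead of 20 mg/day at a constant ruxolitinib starting dose, and 14 instead of 2 mg/day for anagrelide. The factor follows from the formulas alone. The worked figures assume constant dosing for the full 52 weeks, and the consequence assumes the formula is programmed literally.

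The reach is limited to descriptive exposure output: Table 3.1.1, the crossover exposure summary, and Table 3.1.2 if average dose is shown there. Power, type I error, efficacy and compliance are untouched. It should be corrected before the exposure tables are programmed, but it does not threaten the trial's conclusions.

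**What to change.** In the average-daily-dose bullet of SAP 6.4, replace the denominator with duration in days, written out as date of last dose minus date of first dose plus 1 (equivalently, 7 times the duration in weeks). Leave the duration bullet in weeks if that is how duration is to be displayed. Apply the same denominator to the crossover and all-ruxolitinib exposure summaries.

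The cost is one formula in the SAP and one line of code. No data, dose, clinical rule or hypothesis test changes.

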## 6.5. Study Drug Compliance

For subjects in the safety population, overall compliance (%) for ruxolitinib/anagrelide will be calculated for all subjects as follows:

$$\text{Overall compliance (\%)} = 100 \times [\text{total dose actually taken (mg)}] / [\text{total prescribed dose (mg)}]$$

The total prescribed dose is defined as the sum of the doses prescribed by the investigator accounting for dose modifications.

The total actual dose taken will be calculated based on information entered on the drug accountability eCRF. If there is dispensed drug that have not been returned yet, the actual dose taken starting from the dispense date of the unreturned drug will be imputed by the dose taken as reported on the dosing eCRF.

Compliance of ruxolitinib will be summarized descriptively and listed.

## 6.6. Prior and Concomitant Medication

Prior medications and concomitant medications will be coded using the WHO Drug Dictionary. For subjects in the safety population, the number and percentage of subjects with prior and concomitant medications will be summarized by WHO drug class and WHO drug term. In the data listing, each medication will be recorded as prior, concomitant, or both prior and concomitant.

[REDACTED]

## 7. EFFICACY

Appendix F provides a list of data displays.

### 7.1. Efficacy Hypotheses

The primary hypothesis is that ruxolitinib will improve the responder rate compared with anagrelide in subjects with ET who are resistant or intolerant to HU. Cochran-Mantel-Haenszel (CMH) method will be used to test the primary hypothesis at 2-sided of alpha level 0.05.

- $H_0$  (null hypothesis):  $\pi_{\text{ruxolitinib}} = \pi_{\text{anagrelide}}$
- $H_A$  (alternative hypothesis):  $\pi_{\text{ruxolitinib}} \neq \pi_{\text{anagrelide}}$

Where  $\pi_{\text{ruxolitinib}}$  and  $\pi_{\text{anagrelide}}$  are the responder rates in the ruxolitinib and anagrelide groups, respectively.

### 7.2. Analysis of the Primary Efficacy Parameter

#### 7.2.1. Primary Efficacy Analysis

The primary efficacy endpoint is the proportion of subjects who achieve a simultaneous reduction of platelet counts to  $< 600 \times 10^9/L$  and of WBC counts to  $< 10 \times 10^9/L$  for at least 80% (6 out of 7 consecutive visits) of biweekly assessments for 12 consecutive weeks between Week 32 and Week 52. This analysis will be based on the ITT population according to the treatment assigned at randomization. The proportion of subjects who meet the response criteria will be estimated with 95% confidence interval. The CMH test stratified by JAK2V617F mutation status (positive or negative), screening platelet count ( $\geq 1000 \times 10^9/L$  or  $< 1000 \times 10^9/L$ ), and prior anagrelide use (yes vs no) will be applied to compare the 2 treatment groups. The test will be 2-sided at 5% significant level. The overall stratum-adjusted odds ratio, along with its 95% confidence interval, will be presented.

In the analysis of the primary efficacy endpoint, the evaluable scheduled assessments will be used. If no scheduled assessment is available, then the unscheduled assessment closest to the visit target day within the analysis window will be used. If there are 2 unscheduled assessments at the same distance to the target day, then the second one will be used for the evaluation. A window of the target day  $\pm 7$  days will be applied for all unscheduled visits. For example, the target day for Week 32 is at Day 225 ( $= 32 \times 7 + 1$ ).

Missing platelet counts or WBC counts at a visit (with no scheduled visit and no unscheduled visit within window of target day) in the range of at least 12 consecutive weeks of assessment of the primary endpoint will be considered as not achieving platelet control and WBC control during that visit. Subjects who discontinue study treatment without meeting the response criteria will be considered as nonresponders. Subjects who meet the primary endpoint criteria of a response but discontinue study drug before Week 52 will be considered as responders.

### **7.2.2. Subgroup Analyses for the Primary Endpoint**

Subgroups will be formed based on the following subject characteristics and baseline variables for those subjects whose data are available:

- JAK2V617F mutation status at baseline: positive versus negative.
- Prior anagrelide use at baseline: yes versus no.
- MPL mutation status at baseline: positive versus negative.
- CALR mutation status at baseline: positive versus negative.
- Triple-negative status at baseline: yes versus no.
- Platelet count at baseline:  $\geq 1000 \times 10^9/L$  versus  $< 1000 \times 10^9/L$ .
- Sex: male versus female.
- Age:  $\leq 65$  years versus  $> 65$  years.
- Prior thrombosis or hemorrhage: yes versus no.
- CV risk factors at baseline: yes versus no.

Cardiovascular risk factors including smoking, hypertension, hypercholesterolemia, and diabetes.

For each subgroup, the proportion of subjects who meet the primary response criteria will be estimated with 95% confidence interval; Fisher exact test will be performed to compare the 2 treatment groups, and odds ratio and its 95% confidence interval will be presented.

### **7.2.3. Sensitivity and Supportive Analyses for Primary Endpoint**

The primary endpoint will be analyzed using the PP population as a sensitivity analysis to the ITT population. If the JAK2V617F mutation status at randomization is not consistent with the JAK2V617F mutation status collected on the eCRF, additional sensitivity analysis of the primary endpoint will be performed by stratifying the JAK2V617F mutation status collected on the eCRF, screening platelet count, and prior anagrelide use (yes vs no).

#### **7.2.3.1 Additional Sensitivity Analyses for Primary Endpoint**

Excess missing data will affect the validity of the study. All efforts will be made to minimize missing data. In addition, sensitivity analysis will be conducted to assess the impact of the missing data if  $> 10\%$  of subjects with primary endpoint status missing.

### 7.2.3.1.1. Primary Endpoint Status Determination

The primary efficacy endpoint is the proportion of subjects who achieve a simultaneous reduction of platelet counts to  $< 600 \times 10^9/L$  and of WBC counts to  $< 10 \times 10^9/L$  for at least 80% (6 out of 7 consecutive visits) of biweekly assessments for 12 consecutive weeks between Week 32 and Week 52. There are 5 consecutive 12-week periods: Weeks 32 to 44, Weeks 34 to 46, Weeks 36 to 48, Weeks 38 to 50 and Weeks 40 to 52.

For each of the 5 consecutive 12-week periods, 7 scheduled biweekly visits are planned. A subject will be flagged as "Responder," "Nonresponder," or "Nondeterminable" as the following at each period:

- If a subject has  $\geq 6$  visits with platelet counts  $< 600 \times 10^9/L$  and WBC counts  $< 10 \times 10^9/L$ , then this subject is flagged as Responder at this period.
- If a subject has  $\geq 2$  visits with platelet count  $\geq 600 \times 10^9/L$  or WBC counts  $\geq 10 \times 10^9/L$ , then this subject is flagged as Nonresponder at this period.
- If the above 2 conditions are not met for a subject, then this subject is flagged as nondeterminable at this period.
- If a subject discontinued from the study treatment between Weeks 32 and 52, the response status for the periods after the treatment discontinuation will not be assessed.

The primary endpoint status for a subject can be determined as the following:

- If any period is deemed as Responder for a subject, then the primary endpoint status of this subject is Responder.
- If "Nonresponder" is flagged in all assessed periods for a subject, then the primary endpoint status of this subject is Nonresponder.
- Otherwise, the primary endpoint status for a subject cannot be determined and the value will be missing.

If a subject discontinued from the study treatment before Week 32, then the primary endpoint status of this subject is missing.

